Continuous Glucose Monitors: One transcutaneous glucose sensor for the Dexcom G5 will be inserted in the subcutaneous tissue and will provide input to the controller. The sensor is powered by the battery within the transmitter that clips to the sensor and the whole assembly is held to the skin with an adhesive patch and communicates wirelessly with the iLet. If the Dexcom G5 CGM sensor fails for any reason during the experiment it will be replaced promptly. The G5 sensor will be replaced at least every 7 days.

iPhone: The Dexcom G5 app is installed and will run on a stock iPhone. The Dexcom G5 app captures CGM glucose values via Bluetooth Low Energy from the transmitter worn on the body. The Dexcom G5 CGM app on the iPhone allows for calibration and maintenance of the sensor session.

iLet Bionic Pancreas Control Unit: The Gen 3.2 iLet bionic pancreas system receives the same CGM glucose values from the Dexcom transmitter worn on the body. The iLet has an integrated graphical user interface (GUI) and touchscreen display that displays the current CGM glucose, a graphical history of the CGM glucose, and doses of insulin delivered by the control algorithm. The GUI can also be used to input optional meal announcements, designating the size of the meal as “Large for Me” “Typical for Me”, “Small for Me”, or “Tiny for Me”, and the mealtime as the “Start”, “Middle”, “End”, or “Sleeping” periods of the day. This will trigger a partial meal-priming bolus, the size of which will adapt throughout the course of the trial to meet a target of 75% of the insulin needs for that size and mealtime. Participants will be instructed to announce meals in the same way when using the insulin-only and bihormonal configurations of the iLet.

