 - If there is a complete failure of iLet operation and it is anticipated that restarting it will take more than an hour, participants may revert to usual care using their own insulin pump or with insulin injections until the iLet can be brought back online with the help of study staff. Every effort should be made to correct the problem as soon as possible, which should almost always be possible within 12 hours.
- Participants will not change the default glucose target of the bionic pancreas without consulting with the study staff.
- Participants may use the temporary target feature of the bionic pancreas but should use for limited periods and for a specific purpose, such as exercise.

Local Alarms

- All alarm settings will be the same in both study arms.
- Alarms will sound and a visual alert will appear on the screen of the G5 mobile app when the CGM glucose is ≤ 70 mg/dl and the iLet will alarm when the CGM glucose is ≤ 50 mg/dl.
 - Participants will be trained to test their BG with the study glucometer in response to such an alarm and take any necessary measures to treat hypoglycemia.

- Participants will be trained on troubleshooting for various scenarios that could lead to low threshold alarms. For instance, a threshold alarm could be due to true hypoglycemia, inaccurate CGM readings, or a compression artifact at the site of the sensor.
 - The first step for all glucose-related alarms will be to perform a fingerstick BG measurement with the study provided glucometer (provided).
 - If the BG measurement is not consistent with the fact that a threshold alarm has occurred, then the participant will assess the accuracy of the CGM, and the possibility of a compression artifact (they will be trained in the causes and recognition of these events). If a compression artifact is suspected, they will take steps to relieve the pressure on the transmitter. If no compression is suspected, the participant will calibrate the CGM.
 - If the BG measurement is consistent with a low threshold alarm, the participant will treat hypoglycemia with carbohydrate ingestion according to their usual practice. Study staff will recommend the standard of care, 15 grams of rapid acting carbohydrates and re-testing BG in 15 minutes. Study staff will recommend the participant continue to monitor their BG until it returns to normoglycemia, and to contact study staff with any questions or concerns.

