- Participants will be trained on the insertion and use of the Dexcom G5 CGM. Participants will insert their own CGM sensor and study staff will confirm they are doing it correctly.
- Study staff will review all study procedures and policies (including the use of the Dexcom G5, the Contour Next One, the Precision Xtra ketone meter, and the iLet device) and the upcoming visit schedule.
- The Dexcom G5 will be calibrated by the participant using the Ascensia Contour Next One SMBG glucometer, and study staff will confirm they are doing it properly.
- Participants will be trained on the use of the iLet.
- The control algorithm will be initialized with the participant's current weight
- The participant will remove his/her own insulin infusion pump and the participant will set up and start the iLet under the supervision of study staff. Participants will be instructed to not take any further insulin outside of the iLet throughout the study.
- The staff will confirm that the iLet is functioning properly prior to discharging the participant.
- All participants will be given Dexcom G5 CGM sensors, an Ascensia Contour Next One SMBG meter with test strips, ketone meter with strips, insulin, dasiglucagon for the bihormonal study arm, a glucagon emergency kit, an iLet, iLet pigtail adapters and Contact Detach infusion sets (an alternate infusion set may be supplied if the subject is known not to do well with the Contact Detach).

Day 7/Day 1 Visit:

- There may be no washout between the two study arms or the washout period may be up to 7 days.
- At the end of the first 7-day arm, subjects will return to the clinic and answer the post questionnaires for the study arm.
- The body weight, heart rate and blood pressure of the subject will be documented
- Blood will be drawn for a chemistry panel and complete blood count.
- Study staff will review any changes in the participant's medical history or medications to ensure continued eligibility, and any adverse events that may have occurred since their last study visit. Study staff will specifically ask subjects if they had any infusion site reactions or other skin irritation in the past 7 days, and will document any reactions.
- The iLet and the study glucometer will be downloaded. The memory of the iLet will be wiped and

it will be re-initialized for the next study period.

- Participants will replace their CGM sensor and calibrate when prompted if they haven't already.

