- Study staff will review all study procedures and policies (including the use of the Dexcom G5, the Contour Next One, and the iLet) and the upcoming visit schedule.
- The control algorithm will be initialized with the participant's current weight. The participant will set up and start the iLet under the supervision of study staff. Participants will be instructed to not take any further insulin outside of the iLet throughout the study.
- The staff will confirm that the iLet is functioning properly prior to discharging the participant.
- All participants will be given additional supplies as needed.

Final Day 7 Visit:

- At the end of the second 7-day arm, subjects will return to the clinic and answer the post questionnaires for the study arm.
- The body weight, heart rate and blood pressure of the subject will be documented.
- Blood will be drawn for a chemistry panel and complete blood count.
- An EKG will be performed. This EKG will be assessed relative to the baseline EKG to identify any potential changes.
- Any changes to medications or medical history and any adverse events that may have occurred since their last study visit will be documented. Study staff will specifically ask subjects if they had any infusion site reactions or other skin irritation in the past 7 days, and will document any reactions.
- The iLet and the study meters will be downloaded.
- All equipment will be collected and cleaned. The Dexcom G5 transmitter will be cleaned using the validated cleaning and disinfecting procedures.
- A study provider will review the last few hours of glucose trend data and insulin and dasiglucagon on board from the iLet, and assist the participants in resuming their usual diabetes management.

Follow Up Visits

- Subjects will return for a follow up visit 10 days (± 3 days) after the final day 7.
 - Any changes to medications or medical history and any adverse events that may have occurred since their last study visit will be documented. Study staff will specifically ask subjects if they had any infusion site reactions or other skin irritation since their last study visit, and will document any reactions.
 - Blood will be drawn for anti-drug antibodies.
 - If the EKG on the final Day 7 visit showed any changes relative to the baseline EKG, an additional EKG will be performed at this follow up visit.
- Subjects will return for a second follow up visit 25 days (± 4 days) after the final day 7.

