The primary endpoint evaluates if the iLet system performs as designed, receiving CGM signals and delivering drug doses (insulin and, when applicable, glucagon) calculated by the control algorithm with an acceptable degree of reliability and accuracy. No formal test of the primary endpoint is planned.

The null hypothesis tested for the key secondary endpoint is:

The amount of hypoglycemia using the bihormonal configuration of the iLet is equal to the amount of hypoglycemia using the insulin-only configuration of the iLet.

The proportion of time with CGM glucose < 54 mg/dl across days 2-7 estimates the amount of hypoglycemia.

VII.b Sample Size Determination

No formal statistical comparisons have been done for this study. This study is primarily intended to verify that the iLet is operating as expected (based on its design and on bench testing) in each configuration in the outpatient setting. A sample size of 10 subjects in a crossover design is considered adequate for this purpose.

VII.c Populations for Analyses

Adult subjects (≥ 18 years old) with type 1 diabetes.

VII.d Statistical Analyses

VII.d.i General Approach

An intention-to-treat analysis will be performed. Descriptive statistics will be used to summarize patient characteristics and assessments. No formal testing will be conducted to establish superiority. In general, all data will be summarized with descriptive statistics for each treatment group. Unless otherwise specified, continuous data will be summarized by presenting the number of non-missing observations, mean, standard deviation (SD), median, minimum, and maximum. Categorical data will be summarized by presenting the number of patients and percentage for each category. P-values can be displayed to aid interpretation, not for inference. Tables, figures and listings of all primary, secondary and safety endpoints will be created.

Baseline and demographic data will be summarized using descriptive statistics. All comparisons will be between treatments within patients. Listings of individual patient data will be presented.

Data from periods when the bionic pancreas was not in use will be included, if available (Dexcom CGM data may not be available in some failure modes). In cases where an arm was not completed we will use the available data from that arm in the data analysis.

VII.d.ii Analysis of the Primary Efficacy Endpoint

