The primary endpoint is whether the iLet operates as designed during the study arms. An arm will be considered to have successfully met its primary endpoint if each of the following is true during the time that the iLet is powered on over the entire treatment period (days 1–7):

1. The percentage of time that valid CGM glucose readings are captured by the iLet is $\geq 80\%$. Sensor warm-up periods, occasions of failed communication between the iLet and sensor–transmitter unit, or other sensor failure conditions are all counted as times when valid CGM glucose reading are not captured.
2. The percentage of the time that each drug channel (insulin, and if applicable, glucagon) is available is $\geq 95\%$. A channel is considered to be available if a cartridge is successfully loaded, there is no pending occlusion alarm or other system failure to prevent attempting a delivery on that channel, and the cartridge is not yet considered empty.
3. The ratio of cumulative drug doses delivered to cumulative drug doses attempted is between 0.95 and 1.05, inclusive, for insulin and, if applicable, for glucagon. Attempted doses refer to calculated doses that are issued for delivery when the channel is available. Doses delivered refers to the dose amounts reported back by the motor controller after the delivery attempts are completed.

If all three evaluations hold true for a patient’s treatment period, the patient-period is operationally successful. The proportion of patients that are operationally successful will be presented by pump type.

VII.d.iii Analysis of the Secondary Endpoints

The proportion of time spent with CGMG < 54 mg/dl and the mean CGMG are analyzed using methods for paired data. The treatment means and mean difference between treatments will be estimated together with the corresponding 95% confidence interval and compared using a paired t-test for normally distributed data or Wilcoxon signed-rank test for non-normally distributed data. Time < 54 mg/dl and mean glucose will be computed from all available CGM data during days 2-7 for both study arms.

All questionnaire data for patients who have completed a minimum of 4 days with a device will be included. Patients who do not complete a questionnaire will be excluded from the patient analyses. Results will be compared by Wilcoxon signed-rank test.

VII.d.iv Safety Analyses

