- CGMG (CGM glucose) every five minutes from the Dexcom CGM
- All fingerstick BG measurements taken by the subject (meter download)
- Average glucose target used
- Insulin total daily dose from bionic pancreas download
- Glucagon total daily dose from bionic pancreas download
- Timing of meal announcements and size of meals announced from bionic pancreas download
- Time subjects were not under bionic pancreas control
- List of technical faults associated with the bionic pancreas including cause and resolution
- Body weight after each study arm
- Blood pressure after each arm
- Heart rate after each arm
- Skin reactions, if any, after each arm
- EKG after completion of the second arm, and at the first follow up visit if applicable
- Information collected from the daily email survey:

- Number of reported hypoglycemic events requiring carbohydrate intervention
- Total grams of carbohydrates taken to treat hypoglycemia
- Number of severe hypoglycemic events (defined as subject required assistance to treat)
- Mean nausea severity from VAS
- Number of unscheduled insulin cartridge/infusion set changes
- Number of unscheduled glucagon cartridge/infusion set changes
- Alcohol use (mean drinks per day)
- Exercise duration and exposure (duration X intensity)
- Data from questionnaires about attitudes and expectations regarding the bionic pancreas at baseline and on day 7 of each arm.

VIII. Risks and Discomforts

Subjects may experience mild discomfort associated with the insertion of infusion sets and the Dexcom CGM sensor into the SC tissues. The risk of discomfort due to insertion of infusion sets and sensors may be greater than in their lives outside the trial because more infusion sets and sensors are required than are used in usual care.

There is a risk of hypoglycemia. This risk is expected to be less than the risk during the subjects' lives outside of the trial based on data from earlier trials. All of our previous studies have shown that hypoglycemia is significantly reduced in all configurations of the bionic pancreas when compared with usual care.

There is a risk of hyperglycemia. This risk is expected to be less than the risk during the subjects' lives outside of the trial based on data from earlier trials. All of our previous studies have shown that hyperglycemia is significantly reduced in all configurations of the bionic pancreas when compared with usual care.

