There is a risk of headache, nausea or vomiting due to the administration of exogenous glucagon. There is a possible risk of skin rash due to administration of exogenous glucagon. There may be risks of daily, low-level glucagon administration that have not become apparent during trials lasting up to 11 days. Possible risks include changes in body weight, blood pressure or blood chemistries or blood counts, or development of anti-drug antibodies. The magnitude of the other possible risks due to daily administration of small amounts of glucagon are unknown, but are not expected to be high because mean glucagon levels have been in the fasted range in previous trials. Of note, the risk of nausea and vomiting has been low in prior studies. There may be other unknown risks associated with dasiglucagon.

IX. Potential Benefits

It is expected that this protocol will yield increased knowledge about using an automated closed-loop to control the glucose level. This research is one step on the path towards development of a fully closed-loop system, and is particularly important for establishing the safety and efficacy of a bihormonal system for larger and longer future studies. The individual participant may not benefit from study participation.

Based on evidence from previous trials of the bionic pancreas and the design of this trial, subjects enrolled in the study may benefit from a reduction in risk of hypoglycemia and hyperglycemia and a better mean glucose than they typically achieve.

Subjects will be financially compensated for participating in the study.

X. Data and Safety Monitoring

X. a. Monitoring of Source Data

During the experiment, CGM data, insulin dosing data, and glucagon dosing data will be automatically stored in the bionic pancreas device (from which it will be downloaded at intervals). All of the data will be combined in a single database that will be compared against the primary data files for integrity. The computer database will be backed up at least monthly and the backup media stored in a secure location.

Study staff will be encouraged to raise any concerns they may have or problems they have identified at any time. The PI, in consultation with the co-investigators, will decide a course of corrective action, and resolution or progress will be assessed no later than the next meeting.

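### Will CGM readings be lost when the iLet is down, because no visit step exports the G5 app record?

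*Combined protocol and SAP*

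**What the plan says.** Section VII.d.i sets the rule for off-device time: "Data from periods when the bionic pancreas was not in use will be included, if available". It adds in parentheses that some kinds of failure will leave no Dexcom data. Section VII.d.iii then defines the data set for the glucose endpoints: "Time < 54 mg/dl and mean glucose will be computed from all available CGM data during days 2-7 for both study arms".

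On storage, section X.a says that "CGM data, insulin dosing data, and glucagon dosing data will be automatically stored in the bionic pancreas device", to be downloaded at intervals, and that all data are then combined in one database and checked against the primary files. Section VI.d.iv gives the visit steps. At the Day 7/Day 1 visit: "The iLet and the study glucometer will be downloaded. The memory of the iLet will be wiped and" the device is re-initialized. At the final Day 7 visit: "The iLet and the study meters will be downloaded", and all equipment is collected.

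Section VI.c describes a second receiver: "The Dexcom G5 app captures CGM glucose values via Bluetooth Low Energy from the transmitter worn on the body". The iLet is said to receive the same values from the same transmitter. The list of collected data in VII.e.ii has the entry "CGMG (CGM glucose) every five minutes from the Dexcom CGM", with no route given.

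**The concern.** Read together, X.a and VI.d.iv name one store of CGM data and one way of retrieving them, both through the iLet. When the iLet fails completely, section VI.d.iii lets the participant return to their own pump or to injections until it is repaired, "which should almost always be possible within 12 hours". The sensor and phone may go on recording in that time. These are the hours that VII.d.i wants in the analysis, and the device expected to hold them is the one that has failed. The app might hold a copy, yet no visit step collects it.

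The endpoint at stake is the key secondary one. Time below 54 mg/dl is a small percentage, so a few hours of low readings in a gap could visibly change one participant's value. Hours on fallback care are also unlikely to be missing at random, which matters for an analysis described as intention-to-treat.

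**Working it through.** **What the text commits to**

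1. VII.d.i includes off-device data on condition that they are available and says that some will not be. VII.d.iii also speaks of available data. Losing some readings contradicts neither statement.
2. The documents are silent on the app record; they do not say that it will be left behind. In VII.e.ii, insulin dose, glucagon dose and meal announcements are each attributed to the bionic pancreas download, and fingerstick values to the meter download. CGM glucose is attributed to the Dexcom CGM. That contrast leaves the source open.
3. The Remote Monitoring Protocol in VI.d.iii describes round-the-clock CGM telemetry and a cloud service. Its source device and any analytic use are not stated, so it is only a possible further record.
4. At the Day 7/Day 1 visit the iLet is downloaded first and wiped afterwards. The wipe loses nothing that has been downloaded.
5. Time not in use is wider than time with the iLet down. Section VI.d.iii allows removal for up to 1 hour at a time and 2 hours in 24, and an iLet that is disconnected but powered may still log CGM values. The exposed time is mainly that of a failed, powered-down or replaced iLet. The documents give no frequency for these events.
6. The primary endpoint in VII.d.ii counts only time with the iLet powered on, so it does not depend on a second record.

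**Size**

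The plan gives no figure for data loss, so there is none to reproduce. The inputs are:

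- Window: days 2-7 at one reading per five minutes (VII.d.iii, VII.e.ii): 6 × 24 × 12 = 1,728 readings.
- Gap: 12 hours (VI.d.iii), the time within which repair is almost always expected: 12 × 12 = 144 readings.
- Share: w = 144 / 1,728 = 0.0833.
- Time below 54 mg/dl in the earlier insulin-only iLet crossover study (I.e): iLet 0.6% with bracketed values 0.2 and 1.1; usual care 0.6% with bracketed values 0.1 and 1.2. The text does not say what the brackets are. Here they serve as a range.

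Recovering the gap changes a participant's value by

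shift = w × (in-gap % − observed %).

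Since participants may return to usual care during a complete failure, the usual-care range of 0.1% to 1.2% is the closest documented figure for the gap:

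| Observed % | In-gap 0.1% | In-gap 1.2% |
|---|---|---|
| 0.2 | −0.008 | +0.083 |
| 0.6 | −0.042 | +0.050 |
| 1.1 | −0.083 | +0.008 |

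One such outage among ten participants moves the arm mean by a tenth of this, at most 0.008 points either way. The mean paired difference moves by the same amount.

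The harsher case assumes 0% to 10% in the gap; the 10% is an assumption with no source in the documents:

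| Observed % | In-gap 0% | In-gap 10% |
|---|---|---|
| 0.2 | −0.017 | +0.817 |
| 0.6 | −0.050 | +0.783 |
| 1.1 | −0.092 | +0.742 |

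With 0.6% observed, the participant's value becomes 0.55% to 1.38%. The arm mean moves by −0.009 to +0.082 points over all three rows. The shift in the mean grows in proportion to the number of outages.

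**The case for a change.** The best argument for a change is that neither reading of VII.e.ii is complete. If CGM glucose comes from the iLet log, as X.a suggests, readings during a failure may be gone. If it comes from the Dexcom system, the visit lists omit the export. Availability also depends partly on staff: a record that exists and is not collected becomes unavailable through inaction, and staff could collect it for some participants and not for others. Listings of individual data are planned, so a single distorted value would be seen. The remedy would be cheap, at one export per end-of-arm visit and an alignment of two logs.

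Part of this stands. No retrieval route is named for hours when the iLet is down, and no rule says which record takes precedence if two exist. A 12-hour window can also differ from a seven-day summary, so the usual-care range does not bound what one participant might experience.

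The rest is weaker. The documents do not establish that the app keeps its record or that it can be exported, so the recoverable second copy is conjecture. The phone record can have gaps too, since the iPhone needs charging at least daily. A sensor or transmitter failure would affect both records. VII.e.ii also has the time outside bionic pancreas control and the technical faults recorded, so the affected hours can be identified when an individual value is read.

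**Conclusion.** The concern does not call for a change. The plan leaves a data-handling detail unstated, and the conditional wording of VII.d.i and VII.d.iii is consistent with either using a second CGM record where one is obtained or accepting the gap where none is. A competent analyst would look for a Dexcom or cloud record before treating the hours as missing, and would keep the iLet log for the primary criterion on readings captured by the iLet.

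If no second record is used, the conclusions still hold. The primary endpoint is unaffected. The glucose comparisons are descriptive: VII.d.i says p-values may be shown as an aid and not for inference, and VII.b describes a ten-person study meant mainly to verify device operation. One 12-hour outage moves the mean time below 54 mg/dl by about 0.01 points on the documented usual-care range, and by about 0.08 points if 10% of the gap is assumed to lie below the threshold.

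These figures rest on one outage among ten participants, the full 12 hours being lost, and rates from an earlier insulin-only study. The documents give neither an outage frequency nor a corresponding rate below 54 mg/dl for the bihormonal arm.
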